# 7.8 Long-term follow-up assessments

Follow-up assessments will take place at 3 and 6 months.

### 7.9 Qualitative assessments

Within each of the four sites, service user participants (n=40) will be invited to a mid- and post intervention focus group regardless of their levels of engagement with the intervention. The topic guide, developed with our LEAG, and informed by the Theoretical Domains Framework, will focus on the acceptability of the intervention. The focus groups will be facilitated by service user researchers and will explore any barriers and enablers of regular intervention session attendance. The focus groups will be recorded and transcribed for analysis. A study ID will be allocated, and any personal data will be removed to protect confidentiality. For individuals who prefer/request to have individual interviews, we will try our best to accommodate that.

Likewise, intervention facilitators will be invited to take part in a focus group/ an interview focusing on their experience of delivering the intervention, content and utility of training, and any barriers or facilitators to intervention delivery. The interview topic guide will be informed by the Theoretical Domains Framework and Normalisation Process Theory. Interviews/focus groups will be conducted by service user researchers. Interviews/focus groups will be audio-recorded and transcribed. A study ID will be allocated, and any personal data will be removed to protect confidentiality.

# See Appendix A (16.A) for a Schedule of procedures and data collection

### 7.10 Withdrawal criteria

No criteria are set for withdrawing participants who have rights to withdraw from the study at any time.

# 7.11 Storage and analysis of clinical samples

Blood sample from participants will be taken by trained research nurse (or phlebotomist) at the specific NHS Trust/site/hospital phlebotomy service. Storage and analysis for metabolic parameters will be conducted by the laboratory services contracted with each Trust/site according to local policy. Only analysis results for participants identified with study IDs but not any personal data will be sent to the Research Team and such data will be stored together with other research data securely in the Sponsor's database (see Section 11).

The blood sample will be destroyed by the laboratory after completing analysis.

### 7.12 End of trial

The study will end when data collection and analysis are completed.

### 8 TRIAL INTERVENTION

### 8.1 Intervention description

The intervention that is being feasibility-tested in this study has been based on the initial review of the literature and development of the intervention logic model (see Appendix 16.B). The final version of

the intervention will be the main output of the co-production process; however the intervention is likely to comprise:

- a. Manualised training for peer workers adapting the ENRICH peer worker training developed by the team along with an adaptation of Manualised Self Management training developed by the team, and incorporating the Lester UK Adaptation for positive cardiometabolic health resource for mental health nurses (MHN)/healthcare professionals. There will be a short webinar-type training around personalised goal setting for other healthcare and voluntary sector staff who will contribute to group clinics.
- b. 12 fortnightly group clinics over a six-month period (final number, duration and frequency of sessions to be determined), co-facilitated by peer worker and MHN, combining targeted psychoeducation (from GP, community cardiovascular nurse, dietician, occupational therapist, exercise therapist, voluntary sector/ community organisations) with peer-supported self-management skills sessions; (For example a dietician will attend a clinic towards the beginning of the six-month intervention and provide introductory psychoeducation on healthy eating, and introduce recipe and dietary plan resources. Initial, personalised goals will be agreed between participants, facilitators and dieticians. Participants will complete a dietary record two and four months later with the dietician returning for review sessions to develop and refine individual dietary goals. Each group will potentially build a resource of recipes and diet plans as developed locally and reflecting the cultural identity of group members. Similar personalised goal setting and review work will be undertaken with specialist professionals around exercise, and alcohol, smoking and paan use.)
- c. Three one-to-one peer support sessions per participant, bringing experiential knowledge, role modelling and social connection work. Members of this team have piloted a modified, peer-supported version of an established wellbeing mapping intervention, designed to enable and empower connection to people, places and activities that are supportive of each individual in a personalised approach to adopting a more healthy lifestyle;
- d. Strategies to build and maintain peer-to-peer support between group clinic members outside of clinic meetings, such as further in-person meetings/drop-in groups utilising local resources (e.g. Park Walk) or a social media group delivered via Whatsapp or closed Facebook group (operated in accordance with participating NHS Trust's policy) offering fortnightly motivating messages with tips;
- e. Monitoring impact of psychotropic medication on cardiovascular risk (e.g. weight gain) with engaging with GP/ psychiatrist to review/ change medication as indicated;
- f. Signposting to annual health checks, follow-up with GP for shared care plan consultation and referral to treatment and signposting to community-based support as appropriate; and
- g. Group booster session at three months post-clinic to monitor and feedback on maintenance of behaviours/ provide refresher psychoeducation.

### 8.1.1 Peer worker and clinical staff training

Manualised training will be developed, alongside the co-production of the intervention.

All peer workers and clinicians recruited to deliver the intervention will be trained; followed by regular supervision throughout the feasibility study.

Included within the training and the intervention delivery procedures are measures to ensure safety and maximise wellbeing of all participants. We will pay particular attention to incorporate trauma-informed care in our intervention delivery. We will work with peer workers and clinicians, LEAG, and members of our PMG to develop procedures to identify early signs of psychotic episodes, general plan for support which can be individualized for each participant from the outset of them joining the group.

Some options identified for a stepped model of support include: taking a short break at a quiet space on site; taking medication as needed; requesting an earlier review; informing care coordinator or a named family member or close friend for support; or referring to Home treatment or Crisis support team.

For any service user participants re-joining the intervention after a short break due to ill health reasons, the staff delivering the intervention will organize a catch-up with them to ensure they feel comfortable and sufficiently stable to rejoin.

Peer workers and clinicians – although they were already working in the mental health services and are experienced in working with the service user populations - will be provided with regular supervision and support.

# 8.2 Trial restrictions

Not applicable.

# 8.3 Assessment of fidelity against the peer support principles

To ascertain the level of fidelity to the peer support principles framework in delivering the intervention, we will ask the Peer Workers to complete a Peer Support Fidelity Index (PSFI about each individual they support.

### 9 SAFETY MONITORING

### 9.1 Definitions

Term	Definition			
Adverse Event (AE)	Any untoward medical occurrence in a participant to whom a trial intervention has been administered, including occurrences which are not necessarily caused by or related to that product.			
Adverse Reaction (AR)	An untoward and unintended response in a participant to a trial intervention which is related to any dose administered to that participant.			
	All cases judged by either the reporting medically qualified professional or the Sponsor as having a reasonable suspected causal relationship to the trial intervention qualify as adverse reactions.			
Serious Adverse Event (SAE)	A serious adverse event is any untoward medical occurrence that:      results in death     is life-threatening     requires inpatient hospitalisation or prolongation of existing hospitalisation     results in persistent or significant disability/incapacity     consists of a congenital anomaly or birth defect			

	Other 'important medical events' may also be considered serious if they jeopardise the participant or require an intervention to prevent one of the above consequences.
	NOTE: The term "life-threatening" in the definition of "serious" refers to an event in which the participant was at risk of death at the time of the event; it does not refer to an event which hypothetically might have caused death if it were more severe.
Serious Adverse Reaction (SAR)	An adverse event that is both serious and, in the opinion of the reporting Investigator, believed with reasonable probability to be due to the trial intervention, based on the information provided.
Suspected Unexpected Serious Adverse Reaction (SUSAR)	A serious adverse reaction, the nature and severity of which is not consistent with the information about the trial intervention in question set out in the section 9.2.

# 9.2 Operational definitions for (S)AEs

This is a feasibility study for a low risk intervention.

The following are expected adverse events and serious adverse events for the patient population:

- 1. Psychiatric hospitalisation
- 2. Self-harm
- 3. Suicide attempt
- 4. Death from suicide

Adverse events will be monitored throughout the study.

# 9.3 Recording and reporting of SAEs, SARs AND SUSARs

All serious adverse events that are also both 'unexpected' (that is, the type of event is not listed in the protocol as an expected occurrence); and 'related' (that is, it resulted from administration of any of the research procedures) will be reported by sites to the central team and the sponsor for expedited reporting to the DMC/PSC and the Research Ethics Committee.

Any (S)AEs will be reported to the Programme Manager/CI and DMC (played by the Programme Steering Committee) via email confidentially. A CRF will be filled out and a log maintained to record any SAE, SARs and SUSARs

# 9.4 Responsibilities

Principal Investigator (PI):

Checking for AEs and ARs when participants attend for treatment / follow-up.

1. Using judgement in assigning seriousness, causality and whether the event/reaction was anticipated using the protocol approved for the trial.

- 2. Using judgement in assigning seriousness and causality and providing an opinion on whether the event/reaction was anticipated using the protocol approved for the trial.
- 3. Ensuring that all SAEs are recorded and reported to the sponsor within 24 hours of becoming aware of the event and provide further follow-up information as soon as available. Ensuring that SAEs are chased with Sponsor if a record of receipt is not received within 2 working days of initial reporting.
- 4. Ensuring that AEs and ARs are recorded and reported to the sponsor in line with the requirements of the protocol.

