## 10.7 Participant population

All participants who are included within the study will be subjected to the study analysis, regardless of whether or not they received the intervention.

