## 16. APPENDICES

Appendix A - Schedule of procedures and data collection

		Stud	y period	
Timepoint	Enrolment	olment Baseline Post-allocation – i & Allocation delivery & researce		
Enrolment	-1 month	0 month	3 month	6 month
Informed consent	X			
Eligibility screen including socio-	Х			
economic data, medical and psychiatric				
history				
Allocation		X		
Intervention		4		
Usual care plus peer-group intervention				
Assessments				
Waist and hip circumference	Х		Χ	Х
BMI	X		Х	X
Fasting blood Triglycerides	X		X	X
Fasting blood HDL, LDL, total-	Х		X	X
cholesterol				
HbA1c	X		Χ	X
Blood pressure	X		Х	X
QRISK3		x (once only)		
Lifestyle behaviour, measured using:		X	Χ	X
DINE; IPAQ-SR; Cigarette smoking,				
tobacco and betel nut or paan use -				
smoking/paan use status and number				
smoked per day; number of paans				
chewed per week				
Alcohol use with AUDIT-C		Х	X	X
Modified Colorado Symptom Index		Х	Χ	X
EQ5D-5L		X	Χ	Х
PHQ9		X	Х	Х
Generalised Self Efficacy scale		X	Х	X
Lubben Social Network Scale		X	Χ	X
STAR		X	Χ	X
Goal-based outcome tool		X	Χ	X
DIAMONDS Service Use Survey		X	Χ	Х
Accelerometer x 1 week		X	Χ	Х
Adverse events			Χ	Х
Perceived acceptability			Χ	Х

Appendix B - Provisional logic model underpinning co-production of the peer supported group clinic intervention

Inputs	Barriers	Mechanisms	Process measures	Outcomes
Manualised self- management facilitation for participants co- delivered by peer workers and mental health nurses	Lack of belief that change is possible/ lack of motivation & skills Lack of understanding among clinicians of alternative worldviews/ interpretations of illness and healthy lifestyle	Targeted Behavioural Change Techniques; role modelling; social learning; goal setting and monitoring Strong 'patient/provider' relationship	Improved health behaviours (activity/ achievement of personalised goals relating to exercise, diet, alcohol, smoking and paan consumption)	Primary outcome Prevalence (reversal) of metabolic syndrome

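### The AE definition depends on receipt of the intervention and the active check depends on attendance, so AE collection is narrower than the study-long monitoring the protocol promises

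*Protocol*

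**What the plan says.** Six places in the protocol bear on this.

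- **Section 9.1** defines an AE as "Any untoward medical occurrence in a participant to whom a trial intervention has been administered". Adverse reactions, serious adverse reactions (SARs) and SUSARs are likewise tied to the trial intervention. The SAE definition has no such condition: "A serious adverse event is any untoward medical occurrence that" meets one of the seriousness criteria.
- **Section 9.2** states "Adverse events will be monitored throughout the study", with no start, end or method. It names psychiatric hospitalisation, self-harm, suicide attempt and death from suicide under "The following are expected adverse events and serious adverse events for the patient population".
- **Section 9.3** sends unexpected and related SAEs for expedited reporting, and an event counts as related if "it resulted from administration of any of the research procedures".
- **Section 9.4** makes the site investigator responsible for "Checking for AEs and ARs when participants attend for treatment / follow-up", and for reporting every SAE to the sponsor within 24 hours of becoming aware of it.
- **Section 10.7** analyses all included participants "regardless of whether or not they received the intervention".
- **Appendix A** has a row "Adverse events" with two marks. The table is broken in the text available; the marks read as months 3 and 6, with none at enrolment or baseline.

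**The concern.** The definition in Section 9.1 starts counting later than the study starts exposing people to procedures. Consent, the fasting blood sample and the baseline assessments all come before the first group session. Followed as written, a site has no AE to record for a minor harm from those procedures. For a serious harm from them, it meets two different tests of whether the event was caused by the research.

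The second difficulty is how events are found. The expected events named in Section 9.2 can plausibly stop a person attending, yet the only active search described takes place when the person attends. Section 10.6 has the monitoring committee recommend whether to modify or stop the study on safety data at the halfway point. In a study of 40 people, one or two unrecorded events could change what that committee sees.

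**Working it through.** The protocol states no figure on this point, so the check is mainly to apply the rules to cases.

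**Order of events.** Consent precedes eligibility screening (Section 7.1.2). The blood sample is taken at screening, and baseline data follow within 2 weeks (Section 7.6). Appendix A places enrolment at month -1 and baseline with allocation at month 0. The intervention comes after that.

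**Cases under the rules as written.**

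1. *Non-serious event from the screening blood sample.* Section 9.1: not an AE, because no intervention has been administered, and not an adverse reaction. Appendix A: no AE entry until month 3. Section 9.2 implies it should be monitored. The rules conflict.
2. *Serious, unexpected event caused by a screening procedure.* Section 9.1: an SAE, but not a SAR and so not a SUSAR, because it is not due to the intervention. Section 9.3: related and unexpected, so expedited. Section 9.4: the sponsor's expedited duty to the ethics committee is written for SUSARs only. The rules conflict.
3. *Psychiatric admission between consent and the first session.* Section 9.1: an SAE, since that definition has no receipt condition, although strictly not an AE. Section 9.4: reportable within 24 hours of awareness. It is covered once someone knows of it.
4. *Admission after month 3, after which the person leaves the groups but does not withdraw.* An AE and an SAE, reportable on awareness. Section 10.8 keeps the person in six-month follow-up, where Section 9.4 applies the check.
5. *The same person withdraws, or is not reached at six months.* Reportable only if someone happens to learn of it. No record review or other active source is stated.

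Cases 1 and 2 are the definitional gap and case 5 is the ascertainment gap. Cases 3 and 4 are covered.

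**Scale of case 5 (illustration only).** Inputs: 40 participants and 85% retention (Section 10.1). Not retained: 40 × (1 − 0.85) = 6. Section 10.1 says 85% or higher, so 6 is the most that assumption allows.

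Suppose events were found only at attended follow-up, and people not retained had *k* times the event risk of those retained. The share of participants with an event who are not seen is then 0.15*k* / (0.15*k* + 0.85):

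- *k* = 1: 0.15 / 1.00 = 15%
- *k* = 2: 0.30 / 1.15 = 26%
- *k* = 3: 0.45 / 1.30 = 35%
- *k* = 5: 0.75 / 1.60 = 47%

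The values of *k* are assumptions. The other routes to awareness would lower each share, so these are ceilings for the given *k*, not estimates.

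**The case against.** The strongest reply is that the rules can largely stand together. Section 9.4 does not say that events are checked *only* at attendance, and scheduled entries at months 3 and 6 do not bar logging an event when it occurs. SAEs are reportable on awareness, deaths have their own route in Section 9.5, and Section 7.7 collects reasons for dropout and repeats a service use survey at follow-up. Further detail may sit in the Trial Monitoring Plan (Section 9.4) and the standard operating procedures (Section 13.5), which are not shown. The study is classed as no higher risk than usual care.

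Much of this stands, and it rules out several stronger readings that a reader might infer:

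- *That admissions before the first session are lost.* They are SAEs under Section 9.1 and reportable on awareness.
- *That someone who leaves the groups is never checked.* Section 9.4 includes follow-up, and Section 10.8 follows everyone who has not withdrawn.
- *That the observed event rate is biased by a known amount.* The protocol gives no event rates, so any such figure would be assumed.
- *That the main trial would inherit a biased safety rate.* Sections 3.1 and 10.3 list what feeds the main trial, and no AE rate is among it.

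Three things remain. A reporting clock that starts at awareness does not create awareness. A reason for dropout is not AE ascertainment, and a survey completed at follow-up does not reach people who miss follow-up. Operating procedures can add a method of search, but they should not have to override a definition in the protocol.

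**Conclusion.** The point holds in a limited form. As defined, AEs exclude non-serious events between consent and the first session. A serious event caused by a research procedure is related under Section 9.3 but is not a SAR or SUSAR under Section 9.1. Events in people who withdraw or miss follow-up *can* go unrecorded; the protocol does not show that they will be.

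The definitional conflict follows from the text alone and needs no assumption. The ascertainment gap rests on the absence of any stated active source for people not seen, and on reading the Appendix A marks as months 3 and 6. On the protocol's own retention assumption it concerns at most about 6 of 40 people. The change is worth making because the halfway safety recommendation relies on these data and the correction is cheap.

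**What to change.** Reconcile Sections 9.1 to 9.4 and Appendix A as follows.

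- **Window and population:** define AEs from informed consent to the 6-month point for every consented participant, whether or not the intervention was received.
- **Relatedness:** use one definition throughout, covering the intervention or any research procedure, and align the reaction, SAR and SUSAR definitions and the sponsor's expedited duty with it.
- **Schedule:** add an AE entry at baseline in Appendix A.
- **People not seen:** at months 3 and 6, check the clinical record for the events named in Section 9.2 and for hospital admissions, where consent allows.
- **Reporting:** give events per enrolled participant (planned n = 40), split before and after the first session. Because consent precedes screening, list separately any event in someone who consents and is then found ineligible.

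The cost is protocol wording, one schedule entry and a short note check on those of the 40 who are not seen, by sites whose procedures already include extracting clinical notes at screening (Section 7.1.2). The downsides are a few more unrelated events logged and the need to confirm that consent covers record access at follow-up.

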# Chief Investigator (CI) / delegate or PMG members:

- 1. Clinical oversight of the safety of patients participating in the trial, including an ongoing review of the risk / benefit.
- 2. Using judgement in assigning the SAEs seriousness, causality and whether the event was anticipated (in line the protocol).
- 3. Using judgement in assigning whether event/reaction was anticipated or expectedin line with the protocol.
- 4. Immediate review of all SUSARs.
- 5. Review of specific SAEs and SARs in accordance with the trial risk assessment and protocol (see Appendix 16.C).

# Sponsor: (NB where relevant these can be delegated to CI)

- 1. Central data collection and verification of AEs, ARs, SAEs, SARs and SUSARs according to the trial protocol onto a database.
- 2. Reporting safety information to the CI, delegate or independent clinical reviewer for the ongoing assessment of the risk / benefit according to the Trial Monitoring Plan.
- 3. Reporting safety information to the independent oversight committees identified for the trial (i.e. Data Monitoring Committee (DMC) and Programme Steering Committee (PSC)) according to the Trial Monitoring Plan.
- 4. Expedited reporting of SUSARs to the REC within required timelines.
- 5. Notifying Investigators of SUSARs that occur within the trial.
- 6. Preparing standard tables and other relevant information in collaboration with the CI and ensuring timely submission to the REC.

### Programme Steering Committee (PSC):

In accordance with the Trial Terms of Reference for the PSC which has agreed to act as the DMC for the feasibility study, periodically reviewing safety data as the DMC regarding safety issues.

